**PROMINENT Smoking Cessation Study**

First, we will conduct univariate group comparison analysis to assert any outstanding correlations feature-wise. But the high-dimensionality of the feature space will require a meaningful low-rank feature representation. For some features a domain-specific dimensionality reduction method can be applied, e.g., gene expression features may be encoded as eigengenes using gene co-expression network analysis. More general linear dimensionality reduction methods like principal component analysis (PCA, unsupervised) or linear discriminant analysis (LDA, supervised) will complete the study of the feature space structure. From this analysis we will derive a compendium of features that convey the most information about the difference in the risk of tumour development across exposures linked to cancer or with lifestyle changing interventions.

We will then use supervised classification procedures (e.g., logistic regression and/or the more sensitive gradient boosting models) to combine these features into explanatory models able to weigh the relative contribution of each feature to the carcinogenic process. The aim of this part of the analysis is to further include putative additive effects as well as non-trivial feature interactions in relation to carcinogenesis. The labels of the training and test instances will be assigned based on the carcinogenesis endpoints specified above. Models able to discriminate between normal tissue before and after intervention will be built and evaluated. Cross-validation and other statistical information criteria (e.g., AIC) will be employed for model evaluation. In the case of gradient boosting models, local feature explanations (e.g., Shapley Additive Explanations or SHAP) will be derived to render the models interpretable.

The outcome of this statistical analysis will serve as a tool for data integration to learn how combinations of different features predict risk and exposure to promoters. Although we do not intend to translate these models to clinical predictive tools, some of the outcomes of this key line of investigation may well lead into some applicable knowledge for risk prediction. Given that the main goal of these models is to help us learn the molecular features of tumour promotion, we will put special emphasis in developing models that are interpretable, using approaches such as SHAP values that we have used before.

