#### 3.3. Data analysis

The clinical cohort will be stratified according to smoking status at timepoint 3 into a Quit Cohort (stopped smoking for 3 months or more at the time of sample collection) and a Smoking Cohort (smoked within 3 months of sample collection). Analysis of laboratory data will be stratified over time (baseline compared to timepoint three) and according to final cohort categorisation.

Machine learning algorithms will be developed to integrate across all of the features of the multi-omics analysis of normal tissues, to identify the combinations of parameters that contribute most to cancer risk. We will integrate salient features of the dynamics of tissue perturbation by tumour promoters including the clonal structure of tissues, protein and gene expression patterns, and differences in the pattern of infiltration of immune cell populations. In order to understand the association between these features and carcinogenesis. We will study whether they can be used to discriminate between groups of samples before or after intervention. We propose an analysis that is organized in logical steps with increasing degrees of complexity.

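### Section 3.3 picks features by comparing labelled groups before it cross-validates the classifiers; done once in that order, cross-validated discrimination is inflated, and the fold unit also needs stating

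*Protocol*

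**What the plan says.** Protocol section 3.3 sets out an ordered analysis.

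- It opens with a screen that uses the group labels: "First, we will conduct univariate group comparison analysis to assert any outstanding correlations feature-wise".
- Dimension reduction follows. Eigengenes and PCA do not use the labels. The alternative to PCA does: "linear discriminant analysis (LDA, supervised) will complete the study of the feature space structure".
- A feature set is then fixed from that work: "From this analysis we will derive a compendium of features that convey the most information about the difference in the risk of tumour development".
- Classification comes next and combines those features: "We will then use supervised classification procedures".
- Training and test data first appear at this later stage: "The labels of the training and test instances will be assigned based on the carcinogenesis endpoints specified above".
- So does evaluation: "Cross-validation and other statistical information criteria (e.g., AIC) will be employed for model evaluation".

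Two kinds of label are in view. One is time: "Models able to discriminate between normal tissue before and after intervention will be built and evaluated". The other is the quit or smoking cohort: "Analysis of laboratory data will be stratified over time (baseline compared to timepoint three) and according to final cohort categorisation".

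Section 5.2.1 expects about 20% of up to 250 recruits to quit, giving 50 paired samples, and calls the study exploratory. The text does not say whether feature choice is repeated within folds, or whether a fold is made of participants or of samples. It names no separate validation sample.

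**The concern.** Cross-validation estimates out-of-sample performance only if the held-out samples took no part in building the model. Choosing features by their association with the label is part of building it. In the order written, the held-out samples have already influenced that choice, so the classifier is tested on chance differences that they helped to create.

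The pairing adds a second problem. In the before/after model each quitter supplies two correlated samples with opposite labels. If one is held out while the other is in training, the model leans towards the wrong label for the held-out sample. If both samples of a person carry the same cohort label, the error goes the other way.

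At stake is the interpretation. Section 3.3 gives learning the molecular features of tumour promotion as the main goal of these models, and plans SHAP explanations for the boosting models. If noise can give an AUC of 0.8, discrimination does not support reading the chosen features as biology.

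**Working it through.** **The plan's own figure.** 250 × 0.20 = 50 quitter pairs, or 100 samples. This reproduces section 5.2.1.

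**Inputs.** The 50 pairs come from section 5.2.1. The number of features p, the number kept k and the within-person correlation ρ are not in the protocol, which says only that the feature space is high-dimensional. They are assumed: p = 1,000 to 20,000, k = 5 to 50, ρ = 0 to 0.8.

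**Hand calculation.** Take p = 5,000 and k = 20, so the kept share is 20/5,000 = 0.4%. For null features the two-sided cut-off is |z| = 2.88, and the mean |z| beyond it is about 3.17. The standard error of a before/after mean difference is √(2(1−ρ)/50), in units of the feature's SD. The apparent effect per kept feature is d = 3.17 × that standard error. Twenty such features combine to D = √20 × d, and AUC = Φ(D/√2).

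- ρ = 0: d = 3.17 × 0.200 = 0.634; D = 2.84; AUC = Φ(2.01) = 0.98
- ρ = 0.5: d = 3.17 × 0.141 = 0.448; D = 2.01; AUC = Φ(1.42) = 0.92
- ρ = 0.8: d = 3.17 × 0.089 = 0.284; D = 1.27; AUC = Φ(0.90) = 0.82

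These are apparent values. Cross-validating after selection should give somewhat less, because the weights are still estimated in training folds.

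**Simulation, before/after label.** Feature values are √ρ × (person effect) + √(1−ρ) × (sample noise), all standard normal, with no true difference. The top k features by t-statistic enter a ridge logistic regression with 5-fold cross-validation. Entries are mean AUC over 20 to 40 repetitions (12 in the last row). The true value is 0.50.

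| p | k | ρ | Selected once, folds by sample | Selected once, folds by person | Selected in fold, folds by sample | Selected in fold, folds by person |
|---|---|---|---|---|---|---|
| 1,000 | 20 | 0.5 | 0.785 | 0.826 | 0.212 | 0.484 |
| 1,000 | 20 | 0.8 | 0.619 | 0.725 | 0.090 | 0.491 |
| 5,000 | 20 | 0 | 0.953 | 0.955 | 0.498 | 0.496 |
| 5,000 | 20 | 0.5 | 0.853 | 0.880 | 0.198 | 0.496 |
| 5,000 | 20 | 0.8 | 0.698 | 0.773 | 0.067 | 0.495 |
| 20,000 | 20 | 0.5 | 0.894 | 0.913 | 0.170 | 0.501 |
| 5,000 | 5 | 0.5 | 0.762 | 0.778 | 0.296 | 0.504 |
| 5,000 | 50 | 0.5 | 0.932 | 0.942 | 0.131 | 0.510 |
| 20,000 | 50 | 0 | 0.998 | 0.998 | 0.489 | 0.498 |

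The last row is the extreme corner of the assumed ranges. Zero correlation between two samples from one person is implausible, so that row marks a limit and is not an expectation.

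**Simulation, cohort label** (assumed 50 v 50 people, both samples used, p = 5,000, k = 20). Selected once with folds by sample: 0.944 at ρ = 0.5 and 0.966 at ρ = 0.8. Selected once with folds by person: 0.932 and 0.941. Selected in fold with folds by sample: 0.712 and 0.805. Both corrections together: 0.505 and 0.507.

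**Fold unit alone** (20 fixed features, no selection, folds by sample). Before/after AUC is 0.386 at ρ = 0.5 and 0.268 at ρ = 0.8; cohort AUC is 0.576 and 0.606. With folds by person all four lie between 0.499 and 0.513.

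**Label-free route** (5,000 independent null features, 50 pairs, ρ = 0.5 or 0.8, folds by person). PCA on all samples with 10 or 20 components gives AUC 0.50. Choosing 5 of 20 components by label on all data gives 0.51 to 0.52.

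**AIC.** It charges for the parameters in the fitted model, not for the thousands of features searched beforehand. AIC computed after selection therefore does not remove this bias.

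**The case against.** The strongest reply is that the protocol gives a sequence, not an algorithm. A reader might infer that features are definitely chosen on all samples and that folds definitely ignore the pairing. The text states neither. The first is an inference from the order; the second is silence that a statistical analysis plan, not available here, could properly settle. This stands, so the point is conditional. It does not remove the point: the protocol fixes an order, and an analysis plan that followed it literally would carry the leak.

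Second, the univariate step is not expressly called a filter, and the text moves straight to dimension reduction, where PCA and eigengenes ignore the labels and LDA is only an alternative. This also stands, and those routes do not leak through selection. The PCA check is limited, because with independent features the leading components mostly carry between-person variation. The label-based comparison, however, is definite and comes first, and the feature set is drawn from the analysis it belongs to.

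Third, a reader might conclude that pure noise gives near-perfect discrimination. That appears only at the extreme corner of assumed inputs; at ρ = 0.8 with 20 features kept the figure is 0.62 to 0.70. The simulations also used ridge regression, while SHAP is planned only for boosting models.

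Fourth, the study is exploratory, no clinical tool is intended, and the listed outcomes are differences in molecular signals, not AUC. This lowers the severity.

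**Conclusion.** The point holds in conditional form. If the label-based choice of features is made once, in the order that section 3.3 gives, cross-validated discrimination is inflated: about 0.6 to 0.95 for a before/after AUC whose true value is 0.50, with 50 pairs and nothing differing. The size depends on the assumed p, k and ρ; the direction does not change over the ranges tried. The fold unit is a separate matter that pulls the before/after result the other way, to 0.07 to 0.30 when selection is nested, folds are by sample and ρ is 0.5 or more. Neither correction alone is enough when samples are correlated; together they return 0.48 to 0.51.

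The documents do not support saying that the reported results will be wrong, since nested selection and folds by participant are not excluded. Should-fix: the aims are exploratory, but the features are to be read as those of tumour promotion.

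**What to change.** Add to section 3.3, in words such as these: all label-dependent steps (univariate screen, LDA, choice of features, tuning) will be repeated within each training fold, and all samples from one participant will be kept in the same fold. Where quitters are compared with continuing smokers, one TP3-minus-TP1 change vector per person is an alternative that removes the pairing problem.

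A label-permutation null for the whole pipeline is a useful check: swap the two time labels within a person for before/after models, and permute cohort labels between people for cohort models. State that AIC computed after feature selection will not be offered as evidence of discrimination.

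The cost is computing time, a few lines of text, and a lower but honest reported accuracy. No extra participants, samples or visits are needed.

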#### 4. STUDY SETTING

This is a single centre study. Participants will be recruited from:

- **GM-LHC attendees**

- People attending the Greater Manchester Lung Health Check programme.

The LHC is a community-based service using mobile trucks often (but not exclusively) located in supermarket car parks in areas around Greater Manchester. There are rooms within the mobile trucks dedicated to the CURE team (smoking cessation) and the research team. It is anticipated that the baseline sample collection will take place on the mobile truck. We plan to collect follow up samples on the screening truck, however, alternative locations will be considered if more convenient. This might include hospital sites within Manchester University NHS Foundation Trust or the participant's home.

- **MFT-CURE attendees**

- People attending the CURE programme within Manchester University NHS Foundation Trust

The CURE team (smoking cessation) will assess current smokers attending MFT and those willing to participate in the study will be consented and have samples collected in hospital sites.

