### 1. BACKGROUND & RATIONALE

Tobacco smoking is known to increase the risk of cancer in both humans and mouse models. The causal link between smoking and tumours of the lung (1), and up to 14 other cancer types (1, 2), has been well established. While there is compelling epidemiological evidence to link tobacco smoking with cancer risk, the underlying biological mechanisms are not well understood. Importantly, we do not understand how smoking impacts the phenotypes of normal tissues and how it promotes cancer development.

To determine the specific role of tobacco smoking in tumour promotion, we will conduct an observational study to investigate the effect of changes in smoking on tissue biology. Specifically, the PROMINENT Smoking Cessation Study will collect serial samples of buccal and nasal cells from volunteers undergoing a smoking cessation lifestyle modification. The underlying hypothesis is that through the comparison of samples obtained prior to the intervention and at subsequent time points thereafter, we will be able to observe differences in the molecular and clonal architecture of normal tissues. These changes will help us understand the mechanisms by which smoking promotes cancer development and could help identify molecular targets for prevention.

This key line of investigation will identify the changes that occur in human buccal and nasal cells upon smoking cessation, which may underlie the observed decreased risk of cancer development observed in people who cease smoking. A clear contribution of tobacco smoking to the mutation rate in certain tissues has been firmly established (3). However, whether it acts exclusively through a contribution to the somatic variation of tissues, or (in addition, or exclusively) as promoters of tumorigenesis is not well understood. In the case of smoking, there is clear evidence of its role in the development of mutations that are drivers of tumours in the lung and other organs. However, recent evidence suggests that quitting smoking promotes replenishment of the bronchial epithelium from mitotically quiescent cells that have avoided tobacco-induced mutagenesis (4).

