### 1.2. Manchester CURE (stop smoking) Project

Manchester has implemented a vanguard programme of hospital-based tobacco-dependency treatment services. The Manchester CURE project (*Conversation-Understand-Replace-Experts/Evidence-base*) has translated the published evidence base of the effectiveness of hospital-based tobacco dependency treatment (the Ottawa Model of Smoking Cessation and randomised controlled trial data) into a resilient, sustainable, and scalable real-world clinical service model (9-12). The CURE team approach every patient that smokes and offers a review of pharmacotherapy, specialist behaviour change support, and motivational interviewing. A key part of this specialist consultation is also offering and agreeing a treatment and support plan after discharge. The CURE team offer ongoing medications and support following discharge, through regular outpatient consultations (face to face or telephone) for 12 weeks or referral to community services for ongoing support. In a pilot of the CURE project the self-reported 12 week quit rate for current smokers was 22% (13). The CURE project has expanded its reach beyond the inpatient pathway to provide outpatient services and tobacco dependency treatment within the Greater Manchester Lung Health Check Programme. The same core principles are maintained within these programmes which include opt-out referral with immediate on the day specialist assessment to commence treatment and agree a further support package beyond the initial assessment. The clinical team will ask current smokers who wish to quit and are eligible for screening whether they would be interested taking part in the study. Those who express an interest will discuss the study with a member of the research team.

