#### 5.1.2. Exclusion criteria

- **All**
  - Never or former smoker (has not smoked within the last 2 weeks)
  - Carbon Monoxide (CO) reading  $< 5$  ppb
  - Prior history of cancer
- **Lung Health Check attendees**
  - Aged  $< 55$  years
- **MFT-CURE attendees**
  - Aged  $< 40$  years

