## **5.3. Recruitment**

### **5.3.1. Sample identification**

All attendees of the Greater Manchester LHC service or MFT-CURE service who currently smoke are reviewed by a smoking cessation practitioner as part of the CURE team. At their clinical appointment, individuals who wish to stop smoking will be informed of the study by their clinical care team and if interested in taking part in research, will then be directed to discuss the study with a member of the research team who will be based on site. This will either be at the same visit or at another time depending on the preference of the individual.

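### The protocol leaves open that hospital-recruited participants give their baseline sample while admitted or acutely ill, so recovery can confound the before-after change in quitters.

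*Protocol*

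**What the plan says.** Participants come from the Lung Health Check (LHC) and from CURE within the hospital trust. For the second source, section 4 says that "those willing to participate in the study will be consented and have samples collected in hospital sites". Section 1.2 describes the service: "The CURE team approach every patient that smokes and offers a review of pharmacotherapy". It also says that "The CURE project has expanded its reach beyond the inpatient pathway to provide outpatient services", so outpatient work was added to an inpatient service, and that "The CURE team offer ongoing medications and support following discharge, through regular outpatient consultations (face to face or telephone) for 12 weeks".

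Section 5.2.2 recruits consecutive eligible attendees. Section 5.3.1 describes the approach this way: "At their clinical appointment, individuals who wish to stop smoking will be informed of the study by their clinical care team". The exclusions in section 5.1.2 that apply to everyone are smoking status ("Never or former smoker (has not smoked within the last 2 weeks"), a low carbon monoxide reading and prior cancer. The only one specific to CURE is age below 40. Sections 5.4 and 5.4.1 place the baseline sample (TP1) at the study visit and ask nothing about clinical state.

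Under section 5.4.2, a participant who quits has TP3 arranged after at least three consecutive months without a cigarette. The rationale in section 1 rests on the "comparison of samples obtained prior to the intervention and at subsequent time points thereafter". Section 2.2 names the before-after difference as an outcome. Section 3.3 stratifies by time (baseline against TP3) and by final Quit or Smoking Cohort, and plans models that separate tissue before and after the intervention. Section 5.2.1 also seeks TP1-TP3 pairs from people who continue to smoke.

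**The concern.** The planned features in section 3.3 include gene and protein expression and immune-cell infiltration. It is reasonable to expect some of these to move with an acute infection, or with antibiotics or systemic steroids, whatever happens to smoking. A CURE participant sampled during such an episode and again three or more months after quitting contributes two changes at once: cessation and recovery. A paired comparison within quitters cannot separate them, and a classifier trained to tell before from after may use either.

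This is a matter of who is sampled, when, and what is recorded at the time. The data items named in section 3.2 are demographics, smoking behaviour, LHC information, the scan result, cancer details and co-morbidities. Acute illness and medication at sampling are not among them. If they are not captured, a later analysis may be unable to adjust for them.

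**Working it through.** **The plan's own figure.** Section 5.2.1 wants 50 quit pairs at a quit rate of about 20%: 50 / 0.20 = 250, the stated cap. It reproduces. The protocol gives no alpha, power, effect size or SD, so there is no power statement to check.

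**Whether the route is open.** Four statements together:
- CURE serves inpatients as well as outpatients (1.2).
- Its attendees are recruited consecutively and sampled in hospital sites (5.2.2, 4).
- No criterion or sampling rule refers to admission, acute illness or treatment (5.1, 5.4).
- For quitters, TP3 is at least three smoke-free months later (5.4.2).

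The recent-smoking and carbon monoxide criteria narrow the inpatient group but do not rule it out.

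**Size.** Let *f* be the share of pairs with an acutely ill TP1, and *r* the shift from recovery in SDs of the paired change. The documents give neither. Assume *r* = 0.5, *f* = 0.10 to 0.40, SD of change = 1 and 50 quit pairs.

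Before-after bias in quitters = *f* × *r*; standard error = 1/√50 = 0.141.

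| *f* | Bias (SD) | Bias / SE | False-positive rate per feature |
|---|---|---|---|
| 0.10 | 0.05 | 0.35 | about 6% |
| 0.20 | 0.10 | 0.71 | about 11% |
| 0.40 | 0.20 | 1.41 | about 28% |

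The last column is the two-sided 5% paired t-test rejection rate (noncentral t) when cessation has no effect.

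Bias in the contrast of change between cohorts = (*f* in quitters − *f* in smokers) × *r*. With equal shares and equal recovery it is zero. With an assumed 40% against 20% it is 0.20 × 0.5 = 0.10 SD.
- 50 quitters, 50 smokers: SE = √(1/50 + 1/50) = 0.200; ratio 0.5; false-positive rate about 8%.
- 50 quitters, 200 smokers: SE = √(1/50 + 1/200) = 0.158; ratio 0.63; false-positive rate about 10%.

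**Cost of dropping ill pairs from the main analysis.** At *f* = 0.10 to 0.40, 5 to 20 of 50 quit pairs go, leaving 30 to 45. The standard error rises from 0.141 to 0.149-0.183.

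**The case against.** A reader might infer that baseline samples are in fact taken during acute admissions and that recovery will be reported as an effect of cessation. The documents do not support this. No section says that sampling happens during an admission. The reference to a clinical appointment in section 5.3.1 fits outpatients, and the research discussion may take place at another time. The hospital share is not given, and only part of it would be acutely ill. Nor do the documents show that LHC attendees are free of acute illness; no stability condition applies to them either.

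The second objection is that a comparator exists. Continuing smokers from the same sources give the same pairs, so a contrast of change could remove much of the bias, and nothing in the documents shows that ill shares differ between cohorts. This stands as far as it goes. But section 3.3 does not make that contrast the basis for attribution, and cancellation needs equal ill shares and equal recovery.

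Third, adjustment for source is commonly left to an SAP, and the questionnaire and laboratory manual are not shown. So the absence of a source term from section 3.3 is not in itself a fault. What remains is that the protocol does not settle whether inpatients may be sampled, and does not name illness or treatment at sampling among its data.

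Finally, excluding ill pairs outright would take the main analysis below the stated minimum of 50. That is correct, and it is why exclusion belongs in a sensitivity analysis.

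**Conclusion.** The gap is real but conditional. The protocol permits TP1 during an admission or acute illness for CURE participants. Where that happens, the before-after change in quitters mixes recovery and treatment with cessation. The Smoking Cohort protects against this only in part.

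The size cannot be fixed from the documents. Under the assumptions above, the before-after bias runs from slight (0.05 SD, about a third of a standard error) to material (0.20 SD, 1.4 standard errors). A contrast of change with unequal ill shares keeps a smaller residual of 0.10 SD, about 0.5-0.6 standard errors. The shares, the 0.5 SD shift and the unit SD are all assumptions. If few CURE participants are sampled while ill, the effect is negligible, but without recording it nobody could show that.

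**What to change.** 1. In sections 4 and 5.1, state whether inpatients may be sampled at TP1.
2. At each sampling visit, record recruitment source, inpatient status, acute respiratory or oral infection, and recent antibiotic or systemic steroid use. For participants already enrolled, backfill from medical records where the consent in section 3.2 allows.
3. In section 3.3, say that effects are attributed to cessation through the change in the Quit Cohort against the change in the Smoking Cohort, adjusted for recruitment source (LHC or CURE). Keep all pairs in this main contrast.
4. Add a sensitivity analysis that leaves out pairs with an acutely ill TP1 or TP3.

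The cost is a few form fields, one adjustment term and a smaller sample in the sensitivity analysis. Backfilled records will be less complete than data taken at the visit.
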